- Psychiatric diagnosis or symptoms, (eg, hallucinations, major depression, or delusions) that, in the opinion of the investigator, could interfere with study procedures
 - Has a “yes” answer to C-SSRS suicidal ideation items 4 or 5, or any suicidal behavior within 6 months before Screening, at Screening, or at the Randomization Visit, or has been hospitalized or treated for suicidal behavior in the past 5 years before Screening
7. Have any contraindications to MRI scanning, including cardiac pacemaker/defibrillator, ferromagnetic metal implants (eg, in skull and cardiac devices other than those approved as safe for use in MRI scanners) or
- Have any evidence of other clinically significant lesions that could indicate a dementia diagnosis other than AD on brain MRI at Screening.
 - Exhibit other significant pathological findings on central read of the brain MRI at Screening, including but not limited to: an area of superficial siderosis; evidence of cerebral vasogenic edema; evidence of cerebral contusion, encephalomalacia, aneurysms, vascular malformations, or infective lesions; evidence of multiple lacunar infarcts; evidence of stroke involving a major vascular territory; severe small vessel or diffuse white matter disease as defined by a score of 3 on the age-related white matter changes score (Wahlund, et al., 2001); space occupying lesions; or brain tumors (however, lesions diagnosed as meningiomas or arachnoid cysts and less than 1 cm at their greatest diameter need not be exclusionary). (revised per Amendment 03)
8. Subjects who have a history of moderate to severe hepatic impairment (eg, Child-Pugh Class B or C). Any 2 of the following criteria at Screening would exclude the subject: INR \geq 1.7; bilirubin \geq 1.5 \times ULN; albumin < LLN; ascites or hepatic encephalopathy. Please note that a single significant abnormality could meet criteria for moderate impairment. (revised per Amendment 01)
9. Results of laboratory tests conducted during screening that are outside the following limits:
- Absolute lymphocyte count (ALC) below Lower Limit of Normal (LLN) or below 800 per mm³ (whichever is higher); ALC will be derived from the complete blood count (CBC) with differential representing the normal lymphocytes (with atypical lymphocytes removed and presented as a separate count if they are present) and calculated by the white blood cell count \times percentage of lymphocytes. (revised per Amendment 01)

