9.3.3 Removal of Subjects from Therapy or Assessment

The investigator may withdraw the subject from the study at any time for safety or administrative reasons. The subject may stop study drug or withdraw from the study at any time for any reason.

Absolute lymphocyte count from the hematology and differential panel will be monitored during the study. ALC will be derived from the CBC with differential representing the normal lymphocytes (with atypical lymphocytes removed and presented as a separate count if they are present) and calculated by the white blood cell count \times percentage of lymphocytes. (revised per Amendment 01) Should a subject develop a Grade 2 or greater lymphocytopenia (less than $800/\text{mm}^3$), the absolute lymphocyte count test should be repeated as soon as possible with the repeat blood sample drawn no later than 5 calendar days from the date of the original test. (revised per Amendment 03) If confirmed, study drug administration should be interrupted for a minimum period of 2 weeks and for a maximum period of 4 weeks. Restart of study drug may take place only when absolute lymphocyte count returns to greater than LLN. Absolute lymphocyte count will be measured 4 weeks after restart of study drug. Subsequent measurements of absolute lymphocyte counts will follow the schedule of assessments (Table 4) and any results showing a Grade 2 or greater lymphocytopenia (less than $800/\text{mm}^3$) should be handled as above. If a 2nd occurrence of Grade 2 or greater lymphocytopenia (less than $800/\text{mm}^3$), that is confirmed on repeat testing, occurs within 6 months, then the subject should be discontinued permanently from the study drug.

Subjects who develop moderate or severe hepatic impairment (eg, Child-Pugh Class B or C) during the study must discontinue study drug. (revised per Amendments 01 and 02) Moderate or severe hepatic impairment are defined as any 2 of the following criteria: $\text{INR} \geq 1.7$; bilirubin $\geq 1.5 \times \text{ULN}$; albumin $< \text{LLN}$; ascites or hepatic encephalopathy. Please note that a single significant abnormality could meet criteria for moderate impairment. (revised per Amendment 02)

Subjects who develop seizures will be discontinued from study drug. (revised per Amendment 02)

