Concomitant therapy with AChEI or memantine should only be allowed and/or acceptable for the region or country in which the study is being conducted and should follow the local standard of care for symptomatic treatment (revised per Amendment 01). Subjects who are taking AChEI or memantine will be required to be on a stable dose for at least 12 weeks before randomization. Initiation of therapy or changing dose of AChEIs or memantine during the study should be undertaken in compliance with local standard of care for symptomatic treatment of AD. (revised per Amendment 02). Subjects who start on AChEI or memantine

or change their dose during the Treatment Period will be permitted to continue in the study; however, subjects should not undertake cognitive assessments until they have been on a stable dose for at least 4 weeks.

Subjects who are taking other medications will be required to be on a stable dose for at least 4 weeks before randomization, except for medications which are administered as short courses (eg, up to 3 weeks unless discussed and agreed with the Medical Monitor) of treatment (eg, anti-infectives, oral steroids) or which are to be used on a PRN basis. Concomitant medications (including short-term use of benzodiazepines and opiates) which are used on a PRN basis and which are central nervous system (CNS) active and may affect cognitive function are not permitted during a period of 72 hours prior to cognitive testing. (revised per Amendment 03)

For subjects who undergo an LP for collection of CSF: Subjects who are on anticoagulants may have a variable dose but should have stable anticoagulation control for at least 4 weeks before the LP procedure. Subjects may be required to stop their anticoagulant medication prior to CSF collection and then restart this medication after the LP procedure, as per local guidelines.

Either aspirin or clopidogrel (or any other antiplatelet drug which is not aspirin) is permitted in all subjects. Aspirin and clopidogrel (or any other antiplatelet drug which is not aspirin) in combination are also permitted but subjects who are on such a combination of antiplatelet drugs may be required to stop 1 or more of these antiplatelet drugs before the LP procedure and restart after the LP as per local guidelines.

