9.5.1.3.3 CEREBROSPINAL FLUID SAMPLING

Amyloid CSF is 1 of the 2 methods available at screening to determine subject eligibility for the study. (revised per Amendment 02 Subjects that undergo the eligibility CSF sample collection or who consent to the CSF longitudinal substudy will be encouraged to stay at the site after completion of LP for medical observation. CSF sample(s) will be collected by LP (gravity drip method only) after fasting (preferred), or at least 2 hours after the most recent meal. Further guidance for the timing of CSF collection is provided in [Section 9.5.1.4.2](#).

Subjects who provide a CSF sample at Screening for amyloid eligibility purposes, but did not initially consent to the CSF longitudinal substudy may provide consent to the CSF longitudinal substudy at any point in time up to Visit 13 (or ED). INR results should be reviewed for subjects who consent to provide a CSF sample and are on concomitant anticoagulation/antiplatelet therapy, prior to LP; if they are assessed by the investigator to be at risk for bleeding, they are to be excluded from CSF collection. (revised per Amendment 01)

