9.5.1.5.3 LABORATORY MEASUREMENTS

Clinical laboratory tests to be performed, including hematology, chemistry, urinalysis, and CSF are summarized in [Table 2](#). Subjects should be in a seated or supine position during blood collection. [Table 3](#) and [Table 4](#) show the visits and time points at which blood for clinical laboratory tests and urine for urinalysis will be collected in the study.

Table 2 Clinical Laboratory Tests

Category	Parameters
Hematology	Hematocrit, hemoglobin, platelets, red blood cell count, and white blood cell count with differential (bands, basophils, eosinophils, lymphocytes ^a , monocytes, neutrophils), rothrombin time, INR (derived from prothrombin time) and aPTT are to be performed for all subjects as part of Screening and at each visit (revised per Amendments 01 and 02). A prothrombin time and INR should also be performed prior to LP for subjects who consent to provide a CSF sample later in the study (ie, postrandomization) and are on anticoagulation/antiplatelet therapy (revised per Amendment 01)
Chemistry	
Electrolytes	Bicarbonate, calcium, chloride, phosphate, potassium, sodium
Liver function tests	Alanine aminotransferase, alkaline phosphatase, aspartate aminotransferase, gamma glutamyl transpeptidase, direct bilirubin, total bilirubin
Renal function tests	Blood urea/blood urea nitrogen, creatinine
Other	Albumin, cholesterol, globulin, glucose, lactate dehydrogenase, total protein, triglycerides, uric acid
Urinalysis	Bacteria, casts, crystals, epithelial cells, glucose, ketones, occult blood, pH, protein, red blood cells, specific gravity, white blood cells Urinalysis (sent to a central lab at Screening; assessed via dipstick at site during randomization phase)
Other	Viral screen (HCVAb [Hepatitis C] and HBsAg [Hepatitis B]). Viral characterization (HSV-1, HSV-2, and CMV) Serum pregnancy test (at Screening, females of child-bearing potential only) Urine pregnancy test (assessed via a dipstick at site during randomization phase, females of child-bearing potential only) Tests for thyroid function and vitamin B12 Blood samples for immunologic assessments. Some of the immunologic assessment blood sample will be used to prepare isolated PBMCs which will be stored for testing if required. (revised per Amendments 02 and 03) Cerebrospinal fluid sampling (see Hematology [above] for INR testing)

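### The hepatic stopping rule (Section 9.3.3) and exclusion criterion 8 leave their trigger indeterminate, and the INR item is not reconciled with anticoagulant use

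*Protocol*

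**What the plan says.** Protocol Section 9.3.3 is mandatory: "Subjects who develop moderate or severe hepatic impairment (eg, Child-Pugh Class B or C) during the study must discontinue study drug". It then gives the definition, "Moderate or severe hepatic impairment are defined as any 2 of the following criteria", and lists four items: INR at or above 1.7; bilirubin at or above 1.5 times ULN; albumin below LLN; ascites or hepatic encephalopathy. The sentence after the list reads "Please note that a single significant abnormality could meet criteria for moderate impairment". Neither the abnormality nor the meaning of significant is given. Child-Pugh classes B and C are named as examples, but the scoring is not reproduced.

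Exclusion criterion 8 in Section 9.3.2 uses the same list, with "Any 2 of the following criteria at Screening would exclude the subject", followed by the same note about a single abnormality.

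On anticoagulants, Section 9.4.7 says "Subjects who are on anticoagulants may have a variable dose but should have stable anticoagulation control", in a paragraph about subjects who have a lumbar puncture. Table 2 in Section 9.5.1.5.3 says that prothrombin time and INR "are to be performed for all subjects as part of Screening and at each visit". The text that tells the investigator what to do with INR in anticoagulated subjects concerns lumbar puncture only: "if they are assessed by the investigator to be at risk for bleeding, they are to be excluded from CSF collection" (Section 9.5.1.3.3).

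**The concern.** A mandatory stop needs a trigger that every site reads in the same way. Here a count of two is followed by an open-ended allowance for one, to be applied at up to approximately 350 sites (Section 6). One investigator can keep a subject on drug and another can stop the same subject, and both can cite Section 9.3.3. The same holds for eligibility under criterion 8.

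The second difficulty is that the INR item counts whatever its cause. Under the two-item definition, an anticoagulated subject whose INR is at or above 1.7 already has one item met, and an albumin below LLN by any margin supplies the second.

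What is at stake is mainly clean safety data and consistent handling of subjects. Section 9.5.1.5.1 treats a laboratory abnormality that leads to withdrawal of drug as an adverse event, so these stops, where treatment-emergent, would enter the tables of events leading to discontinuation in Section 9.7.1.8.2. In the other direction, the undefined note leaves genuine cases to local opinion, for a drug whose Cmax and AUC were about 91% and 45% higher in moderate hepatic impairment (Section 7.1).

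**Working it through.** No figure in the plan needs reproducing; the point is one of logic. Apply both sentences of Section 9.3.3 to each finding that includes a raised INR.

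| Findings | Two-item definition | Single-abnormality note |
|---|---|---|
| INR at or above 1.7 only | not met | could be met |
| INR plus albumin below LLN | met | could be met |
| INR plus bilirubin at or above 1.5 times ULN | met | could be met |
| INR plus ascites or encephalopathy | met | could be met |
| INR plus two or three of the others | met | could be met |

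- **Row 1** shows the indeterminacy: the definition keeps the subject on drug, while the note allows a stop. The same split arises for any one of the four items occurring alone.
- **Row 2** does not depend on the note. The definition alone is satisfied, and nothing in Section 9.3.3 or criterion 8 asks whether the INR has a hepatic cause.

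**Scale.** The documents give neither the share of anticoagulated subjects, nor their INR, nor the frequency of low albumin. Every rate below is an assumption, applied to N = 1330.

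1. Anticoagulant-raised INR in 1% to 10% of subjects: 1330 × 0.01 = 13 to 1330 × 0.10 = 133. These subjects are exposed to the single-abnormality reading on INR alone.
2. If 2% to 10% of those also have a second listed finding: 13.3 × 0.02 = 0.27 to 133 × 0.10 = 13.3 meet the two-item definition.
3. A harsher set: raised INR in 3% to 10% (40 to 133 subjects), and albumin below LLN at 1% to 3% of the 11 post-baseline treatment visits (Visits 3 to 13), with visits independent. The chance of at least one such visit is 1 − 0.99^11 = 10.5% to 1 − 0.97^11 = 28.5%, giving 40 × 0.105 = 4 to 133 × 0.285 = 38 subjects.

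Step 3 probably overstates. Low albumin tends to cluster within a person, which lowers the chance of at least one occurrence. Criterion 8 also removes anyone who already has both findings at Screening. Taken together, the assumed range is from fewer than 1 to 38 subjects.

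**The case against.** The best reply is that the two sentences can be read together: a working count, plus a caution that the named classification may be reached on one marked abnormality. The note says that one abnormality could meet the criteria, not that it does. That stands, so a reader who infers a flat contradiction goes too far. The note is an undefined second threshold, and it still leaves a mandatory action without a determinate trigger.

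It can also be said that permission for anticoagulants is only implied, because the sentence in Section 9.4.7 belongs to the lumbar puncture paragraph. That is fair as to its setting. But anticoagulants are not in the prohibited listings of Appendix 2, and Section 9.4.7 and Table 2 both provide for anticoagulated subjects in the trial. That these subjects reach an INR of 1.7 is not stated anywhere, and the size of the problem depends on it.

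Other stronger inferences are tempting but not supported:

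- **Permanent discontinuation.** The lymphocyte, infection, rash and herpes rules use that term; the hepatic rule does not.
- **A corrupted count of hepatic discontinuations.** No such count is planned. Contributing reasons for stopping and concomitant medication are both recorded, so affected subjects could be identified.
- **A missing repeat test as an error.** The lymphocyte rule requires one, but whether a hepatic stop should is a clinical choice, and other stopping rules in Section 9.3.3 have none.

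**Conclusion.** The point holds as a defect of wording with practical consequences. The trigger in Section 9.3.3 and criterion 8 is indeterminate between two items and one unnamed item. Independently, the INR item can be met through anticoagulation, so that a subject with INR at or above 1.7 and albumin below LLN is classed as hepatically impaired without liver disease.

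The number affected is unknown; the range of fewer than 1 to a few tens of 1330 rests wholly on assumed rates. A reader might infer a threat to the efficacy conclusion. The documents do not support that: the primary analysis in Section 9.7.1.6.1 disregards adherence, subjects who stop drug are asked back for the 12- and 24-month assessments that remain (Section 9.3.3), and nothing suggests that an anticoagulant-raised INR differs by blinded arm. No sample size, power or alpha figure is affected.

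**What to change.** Reconcile the two-item definition with the single-abnormality note in Section 9.3.3 and in exclusion criterion 8, so that one determinate trigger remains and reads the same in both places. Reconcile the INR item with the anticoagulant use provided for in Section 9.4.7, stating explicitly how an INR raised by an anticoagulant is to be treated under each rule. Which thresholds and causes should count is for the sponsor's medical staff; this review takes no position.

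The cost is amendment wording in two sections, and in any synopsis text that repeats criterion 8. If the sponsor decides that cause matters, sites would also need to document the attribution for anticoagulated subjects.

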9.4 Treatment(s)

9.4.1 Treatment(s) Administered

For this study the test drug is elenbecestat (E2609) and the control drug is placebo. All study drug is to be administered orally, once daily (QD), in the morning with or without food. As shown in [Figure 1](#), there will be 2 treatment arms where the elenbecestat (E2609) arm will be administered a single dose of 50 mg per day and the control arm will be administered placebo.

Study treatment will begin on Day 1 (at the study site) following randomization and will continue for approximately 24 months. Please refer to [Table 4](#) and [Section 9.5.1.4.1](#) for specific information regarding study drug administration on days when PK sampling is to be performed.

Study drug dose will remain the same for each individual subject throughout the duration of the study. If a subject develops a concurrent illness during the treatment period, the investigator should discuss with the medical monitor on whether dosing with study drug needs to be temporarily suspended. As a general clinical guideline, dosing with study drug may be resumed after resolution or stabilization of the concurrent illness, after discussion with the medical monitor.

Rules for discontinuing study treatment for subjects due to skin rash or to severe infections are described in [Section 9.5.1.5.5](#).

9.4.2 Identity of Investigational Product(s)

Elenbecestat (E2609) will be supplied by the sponsor as tablets of 50-mg dose strength in bottles of 35 tablets each. Placebo tablets to match elenbecestat (E2609) will be of identical appearance. Each subject will receive 1 tablet of 50 mg elenbecestat (E2609) or an identical placebo tablet, to be administered orally QD in the morning with or without food. The product release certificates for elenbecestat (E2609) and placebo will be included in the clinical study report for this protocol.

Subjects will be stratified and randomized, and drug will be dispensed, via an interactive voice and web response system (IxRS) system (see [Section 9.4.3](#)).

The sponsor will provide the study drugs packaged in a double-blind configuration. Each subject's study tablets will consist of either elenbecestat (E2609) or placebo (see [Section 9.4.2.3](#) for labeling details).

9.4.2.1 Chemical Name, Structural Formula of Elenbecestat (E2609)

- Test drug code: E2609
- Generic name: elenbecestat (pINN)
- Chemical name: International Union of Pure and Applied Chemistry
N-{3-[(4*aS*,5*R*,7*aS*)-2-Amino-5-methyl-4*a*,5-dihydro-4*H*-furo[3,4-*d*][1,3]thiazin-7*a*(7*H*)-yl]-4-fluorophenyl}-5-(difluoromethyl)pyrazine-2-carboxamide
- Molecular formula: C₁₉H₁₈F₃N₅O₂S
- Relative molecular mass: 437.44

9.4.2.2 Comparator Drug

Not applicable.

9.4.2.3 Labeling for Study Drug

Elenbecestat (E2609) will be labeled in accordance with text that is in full regulatory compliance with each participating country and is translated into the required language(s) for each of those countries. The following information may be included but is not limited to:

- Protocol number
- For clinical study use only
- Name and address of the sponsor
- Chemical name/drug identifier
- Lot number/batch number
- Storage conditions, expiration date if necessary

9.4.2.4 Storage Conditions

Study drug will be stored in accordance with the labeled storage conditions. Temperature monitoring is required at the storage location to ensure that the study drug is maintained within an established temperature range. The investigator or designee (or if regionally required, the head of the medical institution) is responsible for ensuring that the temperature is monitored throughout the total duration of the study and that records are maintained; the temperature should be monitored continuously by using either an in-house validated data acquisition system, a mechanical recording device, such as a calibrated chart recorder, or by manual means, such that minimum and maximum thermometric values over a specific time period can be recorded and retrieved as required.

9.4.3 Method of Assigning Subjects to Treatment Groups

Subjects will be assigned to treatments based on a computer-generated randomization scheme that will be reviewed and approved by an independent statistician. The

randomization scheme and identification for each subject will be included in the final clinical study report for this study. The doses and number of treatment groups to be used are described in [Section 9.4.1](#).

Stratification and randomization will be performed centrally by an IxRS. The IxRS or clinical supply vendor will generate the randomized bottle identification numbers. At enrollment (Screening), the investigator or designee will call the IxRS to register the subject information. At randomization (Visit 2), the IxRS will assign each subject a unique randomization number.

9.4.4 Selection of Doses in the Study

Selection of elenbecestat (E2609) 50 mg per day is based on the results (PD, safety, and tolerability) from the completed Phase 1 studies and interim data from the ongoing Phase 2 Study 202. Study 202 is currently evaluating the PD effects (reduction from baseline in CSF A β levels) of 5, 15, and 50 mg of elenbecestat (E2609) given daily. An interim PD analysis has been performed on the degree of CSF A β reduction achieved with elenbecestat (E2609) 5, 15, and 50 mg per day. Based on the PK/PD modeling results, elenbecestat (E2609) 50 mg per day reduced median CSF A β by approximately 70%. (revised per Amendment 02) Based on these data, elenbecestat (E2609) 50 mg per day dose was selected as a viable dose for this study. Subjects will be stratified according to region (7 levels), clinical dementia staging with no more than approximately 25% of the randomized subjects diagnosed with the early stages of mild dementia due to AD, and concurrent AD medication use.

